### Surveys

Should a participant report emotional distress in responding to survey questions, the research coordinators will refer to [name], who is responsible for overseeing participants' safety and who will recommend follow-up.

### Fitbit

There is no additional risk with using a Fitbit activity monitor for research as compared to using the device as a consumer, including mild skin irritation (i.e. contact dermatitis) which occurs among a small proportion of users. Participants will be instructed via the consent form on methods to reduce irritation (e.g. keep the band clean and dry) and that they can remove the band for a short period of time.

### Loss of Confidentiality or Privacy

All subjects will be informed that their responses are confidential and that they may refuse to participate in the project or withdraw at any time without explanation, and that such action will not affect their future interactions with their health care

providers, employment, educational studies, or the research study. The risk of loss of confidentiality will be minimized by securely storing data including PHI in a Northwell-approved database and minimizing the use of PHI. To ensure confidentiality, all data containing personal identifiers, and used to track contact with patients, will be kept in a secure, password-protected, encrypted Northwell-approved database. No paper documents with personal identifiers will be kept. The PI will be responsible for ensuring that the confidentiality of the data is maintained at all times. All data will be obtained specifically for research purposes.

Personal or identifiable information is not stored on any of the devices used in this study. No information about the participants or the participants' health history will be shared with Fitbit, except for the information the participants directly share themselves should they choose to use the device for personal use at the conclusion of the study. There is no additional risk with using Fitbit as part of this research study as compared to using the device as a consumer.

## 18. RESEARCH RELATED HARM/INJURY

- *Describe the availability of medical or psychological resources that subjects might need as a result of anticipated problems that may be known to be associated with the research.*
- *If the research is greater than minimal risk, explain any medical treatments that are available if research-related injury occurs, who will provide it, what will be provided, and who will pay for it.*

Research-related injuries are not expected for this “no greater than minimal risk” project.

## 19. POTENTIAL BENEFIT TO SUBJECTS

- *Explain what benefits might be derived from participation in the study, noting in particular the benefit over standard treatment (e.g. a once-a-day administration instead of four times a day, an oral formulation over an IV administration).*
- *Also state if there are no known benefits to subjects, but detail the value of knowledge to be gained*

Although not a primary endpoint, participants randomized to the intervention may receive an indirect benefit, i.e., they may gain a better understanding of MBI components impact their sleep duration, and the impact of perceived stress levels on their sleep duration. This may result in their being more satisfied with their

sleep quality wellness regimen and in achieving reduced sleep disturbance symptoms. Through pooling N-of-1 trial data, a greater understanding of the effectiveness of MBI on sleep duration. This knowledge may contribute to the incorporation of N-of-1 trials into the clinical practice of sleep quality management. Additionally, the information collected from participant involvement will inform the development of future personalized trials to help other research participants and eventually patients discover which wellness options are best for them as an individual.

## 20. PROVISIONS TO PROTECT PRIVACY INTERESTS OF SUBJECTS

- *Describe the methods used to identify potential research subjects, obtain consent and gather information about subjects to ensure that their privacy is not invaded.*
- *In addition consider privacy protections that may be needed due to communications with subjects (such as phone messages or mail).*

Names and email addresses from potential study participants will not be collected until they have read through web information explaining the research study and protocol and indicated their interest in the study. This information will be stored in a Northwell-approved database drive to store PHI, and it will only be accessible to research staff listed on the approved IRB protocol. Names or other identifying information will not be shared with those outside the research team, except as indicated in the “Data Management and Confidentiality” section above for the purposes of sending research communications. Phone numbers and email will only be used for study-related communications, and employees will be contacted outside the study for future research opportunities only as indicated in the consent document.

## 21. COSTS TO SUBJECTS

- *Describe any foreseeable costs that subjects may incur through participation in the research*
- *Indicate whether research procedures will be billed to insurance or paid for by the research study.*

This research study is funded by the National Institutes for Aging (NIA). All study devices will be provided to participants at no cost. Participant insurance will not be billed.

This study uses text messaging to deliver notifications, reminders, and study questionnaires. Standard message and data rates from the participant's wireless carrier may apply to the study participant. Study participants will not be compensated for any costs related to data usage or sending or receiving text messages by the study or by members of the study team.

## 22. PAYMENT TO SUBJECTS

- *Describe the amount of payment to subjects, in what form payment will be received and the timing of the payments.*

Study participants who successfully complete baseline will be able to keep their Fitbit device (value \$150). Participants who complete all study activities will receive a \$50 ClinCard as compensation.

## 23. CONSENT PROCESS

*If obtaining consent for this study, describe:*

- *Who will be obtaining consent*
- *Where consent will be obtained*
- *Any waiting period available between informing the prospective participant and obtaining consent*
- *Steps that will be taken to assure the participants' understanding*
- *Any tools that will be utilized during the consent process*
- *Information about how the consent will be documented in writing. If using a standard consent form, indicate such.*
- *Procedures for maintaining informed consent.*

Consent and written authorization will be obtained electronically via REDCap with a copy of the electronically signed form sent to the participants with their study instructions and devices. Before being sent a copy of the consent form, potential participants will view a brief summary of the study, complete a written authorization form, and complete initial screening forms.

If a prospective participant is deemed ineligible, or if the potential participant is eligible but needs to be waitlisted due to demand, the consenting coordinator will notify the potential participant via text within 2 business days of the initial completion date of the pre-screen.

If the potential participant is deemed eligible, potential participants will opt in or out of having a 30-minute virtual call to go over study details with a consenting coordinator and have the opportunity to have any of their questions answered. After the phone call takes place, the consenting coordinator will send the potential participant a link to read and electronically sign the consent form. If the participant opts out of having the call, they will be sent a link to read and electronically sign the consent form. Included at the link sent to participants who opted in and out of the call will be a short, animated video that explains key aspects of the protocol and consent process. Included in these materials will

be contact information to reach a consenting coordinator to answer any additional questions they have before signing the consent form. In order for the consent form to be signed and submitted successfully, potential participants will need to correctly answer 4 questions about the protocol to demonstrate their understanding. PDF versions of signed consent forms will be maintained electronically on a HIPAA-compliant, Northwell Health-approved share drive, accessible only to members of the research team listed on the IRB protocol. A copy of the consent form and signed signature page will be sent to the potential participant along with their baseline study material.

*In the state of NY, any participants under the age of 18 are considered children. If your study involves children, additional information should be provided to describe:*

- *How parental permission will be obtained*
- *From how many parents will parental permission be obtained*
- *Whether permission will be obtained from individuals other than parents, and if so, who will be allowed to provide permission. The process used to determine these individual's authority to consent for the child should be provided*
- *Whether or not assent will be obtained from the child*
- *How will assent be documented*
- *Whether child subjects may be expected to attain legal age to consent to the procedures for research prior to the completion of their participation in the research. If so, describe the process that will be used to obtain their legal consent to continue participation in the study. Indicate what will occur if consent is not obtained from the now-adult subjects.*

**N/A**

*If the study involves cognitively impaired adults, additional information should be provided to describe:*

- *The process to determine whether an individual is capable of consent*
- *Indicate who will make this assessment*
- *The plan should indicate that documentation of the determination and assessment will be placed in the medical record, when applicable, in addition to the research record.*
- *If permission of a legally authorized representative will be obtained,*
  - *list the individuals from who permission will be obtained in order of priority*
  - *Describe the process for assent of subjects; indicate whether assent will be required of all, some or none of the subjects. If some, which subjects will be required to assent and which will not.*
  - *If assent will not be obtained from some or all subjects, provide an explanation as to why not*
  - *Describe whether assent will be documented and the process to document assent*

- *Indicate if the subject could regain capacity and at what point you would obtain their consent for continued participation in the study*

N/A
-----

*If the study will enroll non-English speaking subjects:*

- *Indicate what language(s) other than English are understood by prospective subjects or representatives*
- *Indicate whether or not consent forms will be translated into a language other than English*
- *Describe the process to ensure that the oral and written information provided to those subjects will be in that language*
- *If non-English speaking subjects will be excluded, provide a justification for doing so*

Presently we hope to collect enough information to justify that this methodology offers a scalable, and efficacious means of supporting sleep health in women who are health care workers, and that this pilot will provide data to support larger clinical trials designed to assess efficacy of the given interventions. Injustice has no place in research with human subjects and undermines public trust in science, thus we are committed to enrolling a racially and ethnically diverse population in this protocol and for all research conducted by the Institute for Health System Science. Towards that commitment, we anticipate that many participants interested in this current research project will represent racial and ethnic minority groups, and we intend to advertise the research without restriction. Race and ethnicity (not just English proficiency) are strongly correlated with access to care, environmental exposures, income, employment, and other social determinants of health, which, by definition, affect health outcomes. We will collect information on all of these factors to help inform virtual research delivery and do not believe that focusing on native English speaking participants in this pilot study - those that may be from ethnically and racially diverse populations - will confirm pre-existing bias or will later negatively impact equitable access, participant comprehensibility or research design applicability to the diverse populations that may be solicited for participation in future clinical trials run under an N-of-1 design.

## 24. WAIVER OR ALTERATION OF THE CONSENT PROCESS

*Complete this section if you are seeking an alteration or complete waiver of the consent process.*

- *Describe the possible risks of harm to the subjects involved in this study and explain why the study involves no more than minimal risk to the subject:*
- *Explain why the waiver/ alteration will not adversely affect the rights and welfare of subjects*
- *Explain why it is impracticable to conduct this research if informed consent is required*
- *Explain why it is not possible to conduct this research without using the information or biospecimens in an identifiable form*
- *If appropriate, explain how the subjects will be provided with additional pertinent information after participation. If not appropriate to do so, explain why.*

Since the consent process will be remote and self-directed, it is not practical or feasible for the investigator to sign the consent form in RedCap. As such, we request a **waiver of the investigator's signature** for this research which is no greater than minimal risk. Individuals are encouraged to reach out to the study team via email and/or a direct phone line if they have any questions and prior to signing the consent form.

*Complete this section if you are obtaining informed consent but you are requesting a waiver of the documentation of consent (i.e., verbal consent will be obtained). To proceed with a waiver based on these criteria, each subject must be asked whether they wish to have documentation linking them to this study. Only complete subsection 1 OR subsection 2.*

#### **SUBSECTION 1**

- *Explain how the only record linking the subject to the research would be the consent document.*
- *Explain how the principal risk of this study would be the potential harm resulting from a breach in the confidentiality*
- *Indicate whether or not subjects will be provided with a written statement regarding the research.*

--

#### **SUBSECTION 2**

- *Describe the possible risks of harm to the subjects involved in this study and explain why the study involves no more than minimal risk.*
- *Confirm that the research only involves procedure for which consent is not normally required outside the research context.*
- *Indicate whether or not subjects will be provided with a written statement regarding the research.*

--

## 25. WAIVER OF HIPAA AUTHORIZATION

N/A

***Complete this section if you seek to obtain a full waiver of HIPAA authorization to use and/or disclose protected health information.***

- *Describe the risks to privacy involved in this study and explain why the study involves no more than minimal risk to privacy:*
- *Describe your plan to protect identifiers from improper use or disclosure and to destroy them at the earliest time.*
- *Indicate why it is not possible to seek subjects' authorization for use or disclosure of PHI.*
- *Indicate why it is not possible to conduct this research without use or disclosure of the PHI.*
- *Indicate if PHI will be disclosed outside NSLIJ Health System, and if so, to whom.*  
*Note: PHI disclosed outside NSLIJ Health System, without HIPAA authorization needs to be tracked. Please see guidance at [www.nslij.com/irb](http://www.nslij.com/irb) for information about tracking disclosures.*

--

***Complete this section if you seek to obtain a partial waiver of the patient's authorization for screening/recruitment purposes (i.e., the researcher does not have access to patient records as s/he is not part of the covered entity)***

*Note: Information collected through a partial waiver for recruitment cannot be shared or disclosed to any other person or entity.*

- *Describe how data will be collected and used:*
- *Indicate why you need the PHI (e.g. PHI is required to determine eligibility, identifiers are necessary to contact the individual to discuss participation, other)*
- *Indicate why the research cannot practicably be conducted without the partial waiver (e.g. no access to medical records or contact information of the targeted population, no treating clinician to assist in recruitment of the study population, other)*

--

## 26. VULNERABLE POPULATIONS:

Indicate whether you will include any of these vulnerable populations. If indicated, submit the appropriate appendix to the IRB for review:

- Children or viable neonate*
- Cognitively impaired*
- Pregnant Women, Fetuses or neonates of uncertain viability or nonviable*
- Prisoners*
- NSLIJ Employees, residents, fellows, etc*

- poor/uninsured
- Students
- Minorities
- Elderly
- Healthy Controls

*If any of these populations are included in the study, describe additional safeguards that will be used to protect their rights and welfare.*

This study is enrolling health care workers. Individuals with a supervisory relationship over an employee will not enroll any individual who reports to them in this study. Employee participation or non-participation in this study will have no bearing on an individual's position at Northwell Health.

We do not intend to prevent study personnel or other employees of the Institute of Health System Science who express an interest in the research from participating. However, no supervisory personnel will be able to enroll participants who report to them in this research. We are not intentionally targeting minorities but expect minorities to be part of those eligible for participation.

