## 7. ELIGIBILITY CRITERIA

- *Describe the characteristics of the subject population, including their anticipated number, age, ranges, sex, ethnic background, and health status. Identify the criteria for inclusion or exclusion of any subpopulation.*
- *Explain the rationale for the involvement of special classes of subjects, such as fetuses, pregnant women, children, prisoners or other institutionalized individuals, or others who are likely to be vulnerable. You cannot include these populations in your research, unless you indicate such in the protocol*

- *Similarly, detail exclusionary criteria: age limits, special populations (minors, pregnant women, decisionally impaired), use of concomitant medications, subjects with other diseases, severity of illness, etc.*

Up to 65 participants will be randomized to receive this pilot study protocol. We aim to recruit a diverse pool of participants with varied ethnic and racial backgrounds.

Inclusion:

- Age 40 – 60 years
- Sex assigned at birth-female
- Northwell employee or affiliate
- Self-reported history of short sleep duration (<7h per 24-h period) for at least 3 months
  - After a 2-week run-in, Fitbit verified short sleep duration, and ≥80% adherence of Fitbit wear and survey submission
- Self-report of perceived stress ≥18 using the Perceived Stress Scale (PSS)
- Owns and can regularly access a smartphone capable of receiving text messages
- Owns and can regularly access an e-mail account
- Willingness to wear a Fitbit device

Exclusion:

- Age < 40 or > 60 years old
- Sex assigned at birth- male
- Not a Northwell employee
- No history of short sleep duration or non-adherent to the Fitbit wear and survey submission
- Self report of perceived stress <18 using the Perceived Stress Scale (PSS)
- Women who are pregnant or breastfeeding
- Does not own or cannot regularly access a smartphone capable of receiving text messages
- Does not possess or cannot regularly access an email account
- Deemed unable to complete the study protocol as a result of cognitive impairment, severe medical or mental illness, or active or prior substance abuse
- Planned surgeries within 6 months from study start date
- Participants who have been previously told by a clinician they have mobility limiting health conditions and/or not to engage in walking for 30 minutes, three times per week or yoga

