## 11. RESEARCH PROCEDURES

- *Include a detailed description of all procedures to be performed on the research subject and the schedule for each procedure.*

- *Include any screening procedures for eligibility and/or baseline diagnostic tests*
- *Include procedures being performed to monitor subjects for safety or minimize risks*
- *Include information about drug washout periods*
- *If drugs or biologics are being administered provide information on dosing and route of administration*
- *Clearly indicate which procedures are only being conducted for research purposes.*
- *If any specimens will be used for this research, explain whether they are being collected specifically for research purposes.*
- *Describe any source records that will be used to collect data about subjects*
- *Indicate the data to be collected, including long term follow-up*

Potential participants who self-identify as having poor sleep duration (<7 hrs per 24hrs) will be directed to a study information site with details about the pilot study. Those who are interested in participating in this pilot study will be directed to sign a HIPAA Authorization form before completing an initial screening survey process. The HIPAA Authorization will be electronically signed via RedCap. The initial screening process includes questions pertaining to inclusion and exclusion criteria and administration of the Perceived Stress Scale (PSS). Consenting coordinators will review these data and determine whether a potential participant is eligible to participate. Those who are eligible will receive a link to a short video about key details from the consent form, as well as an electronic copy of the consent form. Potential participants will also be given the option to set up a 30-minute phone call with a research coordinator, where the research coordinator will describe the study process and offer an additional opportunity for the potential participant to ask any questions. After completing or opting out of the phone call, the potential participant will be sent a link to view and electronically sign the consent form in RedCap. Before being able to sign and submit the consent form, potential participants must demonstrate their understanding of the protocol by correctly answering 4 questions pertaining to the information presented in the consent form.

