Ten days into the baseline period, a Consenting Coordinator will review individual adherence to Fitbit wear and survey responses. Adherence to Fitbit wear will be defined as recorded activity of greater than 12 hours a day, and recorded sleeping activity greater than 180 minutes in total. Survey adherence will be defined as submission of a given survey. Baseline participants who do not achieve at least 80% adherence of Fitbit wear and survey submission during the first 10 days of the baseline period will be given until day 14 of the trial to obtain 80% adherence. Those who still do not meet 80% adherence by day 14 will be withdrawn from the study. Those participants who do maintain at least 80% adherence during the baseline period will be randomized to one of two intervention sequences in the pilot study. Participants who are randomized to receive intervention sequences will receive confirmation including their protocol timeline. Enrollment will continue until up to 65 participants have been randomized overall, with the goal of reaching 60 participants who complete research procedures with any post-randomization data: 30 participants randomized to receive ABCCBA and 30 participants randomized to receive CBAABC.

Each intervention sequence is made up of six 2-week periods assigning yoga, mindfulness or guided walking. Participants will be limited to 3 (30 minute) intervention sessions each week. During all intervention weeks (12 weeks total), participants will be asked to continue wearing their Fitbit device each day and night. They will continue to receive EMA surveys bi-weekly with questions about their health such as pain, fatigue, concentration, confidence, mood, and stress at that current moment, as well as a daily morning text asking them to report on their

sleep duration and quality the previous night, using a modified Consensus Sleep Diary. At the end of each intervention period on Sunday evening (every two weeks), participants will also receive the PHQ-4 and Perceived Stress Scale (PSS). A study phone number and email address will be available as part of each survey to contact the study team if a participant is concerned about any side effects they are experiencing. Participants will be instructed to contact 911 or go to the nearest emergency room in the event of a medical emergency.

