### **Sample size justification:**

The primary aim of this study is to evaluate the effect of a personalized MBI on increasing the average daily sleep duration in working at Northwell Health. A sample size of 30 participants per arm achieve 80% power to detect a minimum effect size of 0.7 expected by one of the three Aim 2 interventions. Calculations were based on GEE tests for repeated measures considering a total of 28 daily measurements (4 weeks) per intervention, at a significance level of 0.05. The within subject standard deviation  $\sigma$  is anticipated to be maximum 2h, with an auto-regressive AR(1) base correlation of 0.95 taken at two successive timepoints. Estimated effect size and correlation values were derived from a previous fatigue study that employed similar intervention/design and collected sleep duration as exploratory endpoint.

The **randomization schedule** will be set up by a member of the Institute of Health System Science data team and provided to the data analyst assigned to this trial.. Randomization will occur with a fixed seed value for the purposes of repeatability and auditability, and the list of participants will be split into two groups using a

random shuffle function that takes that seed as input. The order in which an individual becomes eligible for one of these randomizations will determine the placement given (i.e. the first person eligible will be randomized to the intervention order given to participant 1 and continue sequentially). Eligibility is obtained by a participant maintaining at least 80% adherence of survey response, Fitbit wear  $\geq 12$  hours a day 80% of days, and 80% sleep data  $\geq 180$  minutes available through the baseline run-in period. The data analyst will alert the research coordinator of the assigned randomization once a participant becomes eligible during the baseline run-in period. As this pilot is not blinded to study coordinators, this concealed allocation involving the data analyst alerting the study coordinator of intervention assignment will be used to prevent bias by blinding the sequence up until time of randomization.

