### Eligibility, Consent, and Survey Data

Screening and consenting takes place in RedCap. Northwell security-review approved system for collecting and storing research data, including PHI. The study team will have access to all data, including PHI, throughout the study. Data analysis will be done by unique identifier. Coded reports will be given back to the study team, who will identify the document before sending to the participant via encrypted messaging.

The study team takes data confidentiality very seriously. Data collected for this research will be maintained on a HIPAA-compliant Northwell-approved SQL database. All members of the research team with access to identifiable and coded data will be trained and included on the IRB submission for approval. Regular meetings will take place with the PI and other members of the study team to ensure protocol adherence and data accuracy. Data collected for this study will be maintained in its original and unaltered source data state in a Northwell-approved SQL database on a Northwell-approved drive to store PHI indefinitely. Data collected under this research may be used for future research in coded format without additional consent as per the consent form participants sign and with

appropriate IRB approval as required. Any additional data that must be shared will be done so according to the consent form participants signed. Only research staff listed within this IRB submission will have access to identifiable information. Anonymized data may be stored indefinitely for reference following the conclusion of the study. The participant will be made aware of all data collected in the consenting process.

This research is funded by the NIA, thus a Certificate of Confidentiality has been issued for this research. Certificates of Confidentiality (CoCs) protect the privacy of research subjects by prohibiting disclosure of identifiable, sensitive research information to anyone not connected to the research except when the subject consents or in a few other specific situations.

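### Study staff may enrol as participants, so concealment is not guaranteed for whoever makes or holds the randomisation list, and a small, avoidable expectation bias is let in

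*Combined protocol and SAP*

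**What the plan says.** Section 26 (Vulnerable Populations) makes an express choice: "We do not intend to prevent study personnel or other employees of the Institute of Health System Science" from joining. The enrolment limit that follows is that "no supervisory personnel will be able to enroll participants who report to them in this research". The same section adds that taking part or declining has no bearing on a person's job. Section 7 admits any "Northwell employee or affiliate" who meets the other criteria and has no exclusion for study staff.

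Other sections say what those staff do:

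- **Screening eligibility (Section 11):** "Consenting coordinators will review these data and determine whether a potential participant is eligible to participate".
- **Run-in adherence (Section 11):** ten days into baseline, "a Consenting Coordinator will review individual adherence to Fitbit wear and survey responses".
- **Allocation (Section 12, randomisation schedule):** the list is "set up by a member of the Institute of Health System Science data team and provided to the data analyst". It is generated from a fixed seed and used in the order in which people become eligible. The analyst withholds each assignment from the coordinator until randomisation, and this is the stated concealment.
- **Data access (Section 14, eligibility, consent and survey data):** "The study team will have access to all data, including PHI, throughout the study".
- **Accumulating data (Section 15):** aggregate data are reported every two weeks to the group that oversees the study.

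No section bars the list maker, the analyst or the coordinators from taking part. None asks them to step back from their own eligibility or allocation, or has staff participants flagged.

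**The concern.** The supervisor rule protects employees from pressure to enrol. It does nothing about bias when a participant also has a working role in the trial. Two separate matters follow.

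**Concealment.** Section 12 relies on the sequence being unknown until randomisation. A list holder who enrols knows it already, so the safeguard is absent for her.

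**Expectation.** The trial is open and the main estimate is change from the run-in, with no untreated group to subtract from it. Entry uses a self-reported Perceived Stress Scale score. The diary, EMA, PSS and PHQ-4 are self-reported, and Fitbit sleep still depends on behaviour such as time spent in bed. A participant who works on the study, and who may see data as they accumulate, plausibly has a stake that an ordinary employee lacks. Any expectation-driven gain would count as a treatment effect.

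**Working it through.** The plan gives no figure on this point to reproduce. The check is a reading of roles against access, then three calculations for scale.

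**1. Who could know what before randomisation**

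| Role | Access under the plan | Own sequence known in advance? |
|---|---|---|
| Analyst assigned to the trial | Holds the list, releases each assignment | Yes |
| Data-team member who made the list | Knows the list; needs only the running count of people randomised | Yes, or nearly so |
| Consenting or research coordinator | Eligibility, adherence, past assignments; not the list | No; partial prediction at most |
| Other Institute employee with no study role | None stated | No |

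**2. How well could a coordinator predict?** Assume one unblocked list with 30 places per sequence, which is how the Section 12 description of splitting a shuffled list reads. Someone who sees all past assignments and always guesses the sequence with more places left has this expected number of correct guesses, with n = 30:

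n + (4^n / C(2n, n) − 1) / 2 = 34.4 of 60, or 57%.

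Perfect concealment gives 50% and holding the list gives 100%. The coordinator's advantage is slight.

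**3. How far could staff participants move the primary estimate?** Section 12 assesses change from run-in in each arm separately, with 30 per arm. If k of 30 are staff, each with an extra gain of b hours:

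shift in arm mean = k × b / 30.

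Both k and b are assumptions, because the documents give neither.

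- k = 2, b = 0.5 h: 2 × 0.5 / 30 = 0.033 h (2 minutes).
- k = 4, b = 0.5 h: 4 × 0.5 / 30 = 0.067 h (4 minutes).
- Wider range, k from 1 to 6 and b from 0.25 to 1.0 h, all in one arm: 1 × 0.25 / 30 = 0.008 h up to 6 × 1.0 / 30 = 0.20 h.
- The same range over all 60 participants: 1 × 0.25 / 60 = 0.004 h up to 6 × 1.0 / 60 = 0.10 h.

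**4. Against the planned effect.** Section 12 gives a minimum effect size of 0.7 and a maximum SD of 2 h.

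- If 0.7 means hours: 0.033 / 0.7 = 5% and 0.067 / 0.7 = 10%.
- If 0.7 means SD units, the effect is 0.7 × 2 = 1.4 h: 0.033 / 1.4 = 2% and 0.067 / 1.4 = 5%.

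**5. Does lost concealment itself bias the primary estimate?** Section 8 gives the sequences ABCCBA and CBAABC, so both arms receive the same three components, in mirrored order. The primary analysis is of change within each arm, and no between-arm test is specified. Participants receive their timeline once randomised. Early knowledge therefore adds only the order of components during a two-week run-in.

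**The case against.** The case against giving this weight is strong, and most of it stands.

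- **Roles are split.** A reader might infer that study personnel in general decide eligibility, hold the list and see everything, so that concealment fails for every staff participant. The documents do not support that. Coordinators judge eligibility and adherence; the list is made and held elsewhere, and Section 12 keeps it from coordinators. The statement on access to all data stands under eligibility, consent and survey data, and does not say that the schedule is included.
- **Little harm to the primary estimate.** A reader might also infer that broken concealment distorts the change from run-in. With mirrored sequences and within-arm change, no clear mechanism for that appears.
- **Everyone is unblinded.** Excluding a few staff leaves the open, uncontrolled design as it is. No passage shows a larger expectation effect in staff.
- **Numbers may be nil.** A staff participant must be female, aged 40 to 60, have a PSS score of at least 18, have Fitbit-verified short sleep and reach 80% adherence.
- **Other safeguards exist.** Run-in entry uses numeric device thresholds. Analysis is by unique identifier, the identity link has restricted access, and 5% of enrolments are audited.

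These points limit the size of the problem but do not remove it. None of the safeguards stops a list holder from enrolling, and entry still depends partly on a self-reported score.

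**Conclusion.** The point holds in a limited form. Admitting study staff is a stated rule, not a missing detail. It leaves concealment unguaranteed for the list maker and the analyst, and only for them. Allowing staff with eligibility, adherence or data-access roles to take part adds a small, avoidable source of expectation bias, more relevant to the self-reported measures than to Fitbit sleep.

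The effect on the primary Fitbit estimate is probably minor: 0.03 to 0.07 h in an arm mean, if 2 to 4 of 30 are staff and each gains an extra 0.5 h. Both inputs are assumed. The documents do not support a claim that the trial's concealment fails generally or that the primary result is materially biased. This is a cheap improvement, worth making because the bias is easily avoided.

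**What to change.** Replace the Section 26 sentence and add an exclusion to Section 7, for example: *Persons listed on this study's IRB submission, and members of the Institute data team with access to the randomisation schedule or to participant data, may not take part. Other employees of Northwell and of the Institute remain eligible.* The rule is easy to apply, because Section 5 already requires all staff who assist with the study to be listed on the submission.

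If any such person has already enrolled, flag her in the data set, state whether she had access to the schedule, and repeat the primary analysis without her.

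The cost is one exclusion line and a handful of lost candidates. Section 5 counts over 79,000 employees, and at most 65 participants are to be randomised.
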